### **10.5.3.4 Other safety data**

#### **ECG**

- shift table baseline to worst on-treatment result for overall assessments
- listing of ECG evaluations for all patients with at least one abnormality.

#### **Vital signs**

Definitions of notably abnormal results will be specified in the RAP.

- shift table baseline to worst on-treatment result

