2.8.3 Vital signs, weight and physical examinations

Vital sign assessments are performed in order to characterize basic body function. The following parameters are collected: systolic and diastolic blood pressure (mmHg), pulse rate (beats per minute), body temperature (°C), and weight (kg).

Vital signs collected during on-treatment period will be summarized. Values measured during the post-treatment period will be flagged in the listings. The number and percentage of patients with notable vital sign values (high/low) will be presented by treatment. For analysis of vital signs, the clinically notable vital sign criteria are provided in [Table 2-5](#).

Table 2-5 Criteria for notable vital sign values

Vital sign [unit]	Notable high value	Notable low value
Systolic blood pressure [mmHg]	≥180 mmHg with increase from baseline of ≥20 mmHg	≤90 mmHg with decrease from baseline of ≥20 mmHg
Diastolic blood pressure [mmHg]	≥105 mmHg with increase from baseline of ≥15 mmHg	≤50 mmHg with decrease from baseline of ≥15 mmHg
Pulse rate [bpm]	≥100 bpm with increase from baseline of >25%	≤50 bpm with decrease from baseline of >25%
Body temperature [°C]	≥ 39.1	--
Weight [kg]	≥10% increase from baseline	≥10% decrease from baseline

Vital signs shift table based on values classified as notable low, normal, notable high or notable (high and low) at baseline and worst post-baseline will be produced.

Descriptive statistics will be provided for baseline, for worst post-baseline value and change from baseline to worst post-baseline value for each vital sign measure.

Patients with any clinically notable vital sign value will be listed.

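### For four of the five vital signs, the baseline side of the SAP's shift table can only read normal, because the notable criteria require a change from baseline

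*Protocol*

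**What the plan says.** Protocol 10.5.3.4 (Vital signs) promises a "shift table baseline to worst on-treatment result" and adds: "Definitions of notably abnormal results will be specified in the RAP".

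SAP 2.8.3 supplies the definition: "For analysis of vital signs, the clinically notable vital sign criteria are provided in" Table 2-5. The same section specifies the table as follows: "Vital signs shift table based on values classified as notable low, normal, notable high or notable (high and low) at baseline and worst post-baseline". It gives no separate rule for classifying a baseline value.

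Table 2-5 uses three kinds of criterion:

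- **Absolute limit and change from baseline.** Systolic pressure: high is "≥180 mmHg with increase from baseline of ≥20 mmHg", low is "≤90 mmHg with decrease from baseline of ≥20 mmHg". Diastolic pressure: high is "≥105 mmHg with increase from baseline of ≥15 mmHg", and low is at most 50 mmHg with a fall of at least 15 mmHg. Pulse: high is "≥100 bpm with increase from baseline of >25" per cent, and low is at most 50 bpm with a fall of more than 25%.
- **Change alone.** Weight: a rise or fall of at least 10%.
- **Absolute limit alone.** Body temperature: at least 39.1 °C, high side only.

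SAP 4.1 makes baseline a single value, in general the last one available before the first treatment.

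SAP 2.8.3 also plans the number and percentage of patients with notable values, a listing of those patients, and descriptive statistics for baseline, worst post-baseline value and the change between them.

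**The concern.** A shift table is meant to separate abnormality that a patient brought into the study from abnormality that arose on treatment. That needs a classification of the baseline value that does not depend on baseline itself. Applied to a baseline value, a criterion that includes a change from baseline can never be met.

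Two things follow. First, for the affected parameters all patients fall in one baseline row, so the table adds nothing to the notable-value counts. Second, for blood pressure and pulse, patients who enter beyond the SAP's own absolute limits are labelled normal at baseline. They stay labelled normal on treatment unless they also move by the required amount.

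Vital signs are part of the secondary safety endpoint (Protocol Table 3-1, SAP 1.2). The low side has some relevance too: Protocol 6.3.4 notes that hypotension has been seen during infusions of monoclonal antibodies.

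**Working it through.** The plan gives no figure to reproduce; this is a logical check of Table 2-5.

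**Step 1. Classify a baseline value.** At baseline, change = value − baseline = 0, and percent change = 0%.

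| Parameter | Change required for notable | Met at change = 0? | Classes possible at baseline |
|---|---|---|---|
| Systolic | ≥20 mmHg either way | No | Normal only |
| Diastolic | ≥15 mmHg either way | No | Normal only |
| Pulse | >25% either way | No | Normal only |
| Weight | ≥10% either way | No | Normal only |
| Temperature | None | Not applicable | Normal, notable high |

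Setting the value equal to baseline over wide ranges confirms this. All 201 whole-number systolic values from 60 to 260 mmHg are normal, as are all 131 diastolic values from 30 to 160 mmHg, all 171 pulse values from 30 to 200 bpm and all 171 weights from 30 to 200 kg. For temperature from 34.0 to 42.0 °C in steps of 0.1, 51 values are normal and 30 (39.1 and above) are notable high. So the baseline side collapses for four of five parameters.

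**Step 2. Classify pairs of values**, first as the SAP is written and then by the absolute limits of Table 2-5 alone.

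| Baseline → later value | Change | SAP as written | Absolute limits only |
|---|---|---|---|
| Pulse 110 → 130 | 20/110 = +18.2% | normal → normal | high → high |
| Pulse 120 → 150 | 30/120 = +25.0%, not >25% | normal → normal | high → high |
| Systolic 185 → 204 | +19 | normal → normal | high → high |
| Systolic 185 → 205 | +20 | normal → notable high | high → high |
| Systolic 88 → 69 | −19 | normal → normal | low → low |
| Systolic 88 → 68 | −20 | normal → notable low | low → low |
| Temperature 39.5 → 37.0 | −2.5 | notable high → normal | high → normal |

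In the six pulse and systolic rows the patient enters beyond the SAP's own limit and is called normal at baseline. The temperature row is a genuine shift, and the SAP handles it correctly.

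The systolic 185 → 205 row shows why both classifications are needed. Absolute limits describe where the patient started and ended. The joint criterion picks up the 20 mmHg rise.

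**Step 3. Compare with the laboratory tables.** SAP 2.8.2.3 builds its laboratory shift tables on CTCAE grade or on low/normal/high, which a baseline value can take in its own right. The notes to Table 4-3 even drop the comparison with baseline when creatinine and fibrinogen are graded. The vital-sign table is the exception.

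**The case against.** Several points on the other side are sound.

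- **Joint criteria are reasonable in themselves.** Requiring both a limit and a change already adjusts for baseline, and it is a sensible way to count newly notable patients. This stands, and those counts should not be altered.
- **A reader might infer that the table cannot work, or that nobody can be notable at baseline.** The documents do not support that. Temperature has an absolute limit and a working shift table, and the post-baseline column is valid for every parameter.
- **A reader might cite systolic 178 → 195 as baseline mislabelling.** It is not: 178 is below 180 and is normal under either classification. It prints as normal to normal because a rise of 17 mmHg misses the 20 mmHg criterion, and whether it should count as a post-baseline abnormality is a design choice.
- **Other outputs cover much of the ground.** The descriptive statistics show entry levels and change, and individual safety assessments are listed. This limits the harm. It does not restore patient-level transitions, and the listing of notable patients uses the same criteria, so pulse 110 → 130 would not appear there.
- **Few patients may enter with extreme pressures.** Protocol 5.3 excludes uncontrolled hypertension and clinically significant arrhythmia, and the documents give no entry distribution. This is fair for high blood pressure. A pulse of 100 bpm or more is not excluded as such, so pulse is the realistic case.
- **Table shells and dataset specifications exist (SAP 1) and were not available.** They might classify baseline differently. If so, they would depart from the SAP sentence, which would still need correcting.

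**Conclusion.** The point holds for four of five parameters, and the label is *wrong as written*: SAP 2.8.3 states a rule, and the rule yields an uninformative baseline. For systolic pressure, diastolic pressure and pulse it also labels as normal any patient who enters beyond the SAP's limits. For weight there is only redundancy, since Table 2-5 has no absolute weight limit by which an entry value could be extreme.

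Severity is minor. One secondary descriptive safety table is affected; nothing in the primary analyses depends on it. A reader might go further and say that haemodynamic safety is misreported. The documents do not support that, because the notable-value counts and descriptive statistics remain valid. Nor is the protocol at fault: its text is sound and defers the definition, so the correction belongs in SAP 2.8.3.

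The conclusion assumes that the SAP sentence is applied literally, with Table 2-5 as the only definition of notable and one baseline value per patient. The number of patients affected cannot be stated from the documents.

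**What to change.** In SAP 2.8.3, for the shift table only:

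1. Classify both the baseline and the worst on-treatment value by the absolute limits already in Table 2-5: systolic ≥180 / ≤90 mmHg, diastolic ≥105 / ≤50 mmHg, pulse ≥100 / ≤50 bpm, temperature ≥39.1 °C. Label the classes low, normal and high rather than notable, so that they are not confused with the joint criteria. Use the combined low-and-high class after baseline only, since a single baseline value cannot be both.
2. Say on-treatment rather than post-baseline, to match the protocol.
3. Take weight out of the shift table and report its percent change from baseline.

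Keep the joint absolute-plus-change criteria unchanged for the count and listing of notable values. A footnote should say that the two outputs use different definitions, because a patient can be high in the shift table without being counted as notable.

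The cost is a small change of SAP wording and one table shell. No new data and no new cut-offs are needed.

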### **10.5.3.5 Supportive analyses for secondary objectives**

Not applicable.

### 10.5.3.6 Tolerability

Tolerability of study treatment will be assessed by summarizing the number of treatment dose interruptions and dose reductions. Reasons for dose interruptions and dose reductions will be listed by patient and summarized ([Section 10.3](#)).

### 10.5.3.7 Pharmacokinetics

The pharmacokinetic parameters that will be assessed are presented in [Table 10-1](#).

**Table 10-1 Pharmacokinetic Parameters to be analyzed**

AUClast	The AUC from time zero to the last measurable concentration sampling time (tlast) (mass x time x volume  )
AUCinf	The AUC from time zero to infinity (mass x time x volume  )
Cmax	The maximum (peak) observed plasma, blood, serum, or other body fluid drug concentration after single dose administration (mass x volume  )
Tmax	The time to reach maximum (peak) plasma, blood, serum, or other body fluid drug concentration after single dose administration (time)
T1/2	The elimination half-life associated with the terminal slope ( $\lambda_z$ ) of a semi logarithmic concentration-time curve (time). Use qualifier for other half-lives
CL	The total body clearance of drug from the plasma (volume x time  )
Vz	The apparent volume of distribution during terminal phase (associated with $\lambda_z$ ) (volume)
AR	Accumulation Ratio=Cmax (multiple Dose)/Cmax (single dose)

PAS will be used in all pharmacokinetic data analysis and PK summary statistics. PK data from Japanese patients treated on the single agent Japanese dose escalation (Arm C) will be analyzed separately.

#### Pharmacokinetic variables:

The following pharmacokinetic parameters will be determined by profile using non-compartmental method(s) for single agent LAG525, LAG525 in combination with PDR001 and PDR001 in combination with LAG525:

- AUCinf, AUClast (AUC0-336h), Cmax, Tmax, T1/2, CL, Vz and accumulation ratio.

Biofluid concentrations will be expressed in mass per volume units. All concentrations below the limit of quantitation or missing data will be reported as such in the concentration data listings. Concentrations below the limit of quantitation will be treated as zero in summary statistics.

Descriptive statistics of all pharmacokinetic parameters will include arithmetic and geometric mean, median, SD, and CV, geometric CV, minimum and maximum. Zero concentrations will not be included in the geometric mean calculation. Since Tmax is generally evaluated by a nonparametric method, median values and ranges will be given for this parameter.

Summary statistics will be presented for LAG525 serum concentrations at each scheduled time point. Descriptive graphical plots of individual serum concentration versus time profiles and mean concentration versus time profiles will be generated.

[figure not shown]
Missing concentration values will be reported as is in data listings. Concentration values below Lower limit of quantitation (LLOQ) will be handled as zero in summary statistics, and reported as is in data listings. Any missing pharmacokinetic parameter data will not be imputed.

[figure not shown]
Further analyses may be conducted using population PK approaches. [REDACTED]

[REDACTED] Any analyses performed will be specified either in the RAP prior to clinical database lock or in a stand-alone analysis plan document. All analyses will be reported either in the CSR or a stand-alone report.

### **Dose proportionality**

The analysis of dose proportionality will be conducted for AUC and Cmax of single agent LAG525, LAG525 in combination with PDR001 and PDR001 in combination with LAG525 using a power model on log-transformed scale. The log-transformed PK parameters will each be regressed onto a fixed factor for log (dose). The 90% confidence interval (CI) of the slope for each PK parameter will be computed from the model and presented in a summary table.

### **10.7 Interim Analysis**

No formal interim analyses are planned.

However, in phase I, the dose-escalation design foresees that decisions based on the current data are taken before the end of the study. More precisely, after each cohort in the dose

escalation part, the next dose will be chosen depending on the observed data (based on safety, tolerability, PK, PD and efficacy data, guided by the recommendations from the BLRM of DLT using EWOC, and recommendations from participating investigators). Details of this procedure and the process for communication with Investigators are provided in [Section 6.2.3](#).

Data from patients in the phase II part will be reviewed on an ongoing basis to monitor the safety and tolerability of the RP2D in that part of the study. The sample size in any of the 16 groups (1 to 16) may be extended to approximately 40 patients, if at least 3 patients have a response (PR or CR) per RECIST 1.1 or irRC for NSCLC, melanoma, renal cancer and mesothelioma, and if at least 2 patients have a response (PR or CR) per RECIST 1.1 or irRC for TNBC. The Investigators and Novartis study personnel will make the decision based on a synthesis of all relevant data available including safety, PK [REDACTED] information.

## 10.8 Sample size calculation

### Phase I

Cohorts of 3 to 6 evaluable patients will be enrolled in the dose-escalation part including at least six patients at the MTD(s)/ RP2D(s) level, as described in [Section 6.2.3](#). Multiple cohorts may be sequentially enrolled to the same dose level. Additional cohorts of 1 to 6 patients may be enrolled at any dose level below the estimated MTD(s)/ RP2D(s) for further elaboration of safety and pharmacokinetic parameters as required. At least 21 patients are required to be treated in the single agent LAG525 dose escalation (Arm A), at least 12 patients are required to be treated in the Japanese dose escalation (Arm C), and at least 15 patients are required to be treated in the combo dose escalation (Arm B), for the model to have reasonable operating characteristics relating to estimation of the MTD.

### Phase II

Approximately 20 patients will be initially enrolled to each of the groups 1 to 16. Any of the 16 groups may be extended to approximately 40 patients.

#### Single-agent LAG525 (groups 1 to 5 and group 11):

Assume that efficacy will be claimed for single agent LAG525 if observing an ORR of  $\geq 20\%$  for NSCLC or renal cancer and  $\geq 30\%$  for Melanoma, the operating characteristics of the design are provided in [Table 10-2](#), including the probability of stopping the enrollment at 20 patients (fewer than 3 responses in the first 20 patients), and the probabilities to extend the enrollment to 40 patients and observe an ORR  $\geq 20\%$  and  $\geq 30\%$ .

Specifically,

- If the true ORR is 10% for NSCLC or renal cancer (i.e. in the unacceptable efficacy range), the probability of observing an ORR  $\geq 20\%$  is 3.8% (< 5%).
- If the true ORR is 15% for melanoma (i.e. in the unacceptable efficacy range), the probability of observing an ORR  $\geq 30\%$  is 1.2% (< 5%).
- If the true ORR is 30% for NSCLC or renal cancer (i.e. in the clinically significant efficacy range), the probability of observing an ORR  $\geq 20\%$  is 92.6%.

- If the true ORR is 40% for melanoma (i.e. in the clinically significant efficacy range), the probability of observing an ORR  $\geq 30\%$  is 92.8%.

**Table 10-2 Operating characteristics of the design (single agent LAG525)**

True ORR	Probability to observe <3 responses in first 20 patients	Groups 1,3,4 and 11: NSCLC and Renal cancer	Groups 2 & 5: Melanoma
		probability to observe an ORR $\geq 20\%$ with 40 patients	probability to observe an ORR $\geq 30\%$ with 40 patients
10%	67.7%	3.8%	< 0.1%
15%	40.5%	22.5%	1.2%
20%	20.6%	53.1%	8.7%
25%	9.1%	78.8%	28.4%
30%	3.5%	92.6%	55.8%
40%	0.4%	99.5%	92.8%

**Combination LAG525+PDR001 (groups 6 to 10 and groups 12 to 16):**

Assume that efficacy will be claimed for the combination of LAG525 + PDR001 if observing an ORR of  $\geq 30\%$  for NSCLC or renal cancer or mesothelioma,  $\geq 20\%$  for TNBC and  $\geq 45\%$  for melanoma, the operating characteristics of the design are provided in [Table 10-3](#) and [Table 10-4](#), including the probability of stopping the enrollment at 20 patients (fewer than 3 responses in the first 20 patients for NSCLC, renal cancer, melanoma and mesothelioma and fewer than 2 responses in the first 20 patients for TNBC), and the probabilities to extend the enrollment to 40 patients and observe an ORR  $\geq 30\%$  (for NSCLC, renal cancer, mesothelioma), 20% (for TNBC) and  $\geq 45\%$  (for melanoma).

Specifically,

- If the true ORR is 15% for NSCLC, mesothelioma or renal cancer (i.e. in the unacceptable efficacy range), the probability of observing an ORR  $\geq 30\%$  is 1.2% (< 5%).
- If the true ORR is 30% for melanoma (i.e. in the unacceptable efficacy range), the probability of observing an ORR  $\geq 45\%$  is 3.2% (< 5%).
- If the true ORR is 40% for NSCLC, mesothelioma or renal cancer (i.e. in the clinically significant efficacy range), the probability of observing an ORR  $\geq 30\%$  is 92.8%.
- If the true ORR is 55% for melanoma (i.e. in the clinically significant efficacy range), the probability of observing an ORR  $\geq 45\%$  is 92.3%.
- If the true ORR is 10% for TNBC (i.e. in the unacceptable efficacy range), the probability of observing an ORR  $\geq 20\%$  is 4.1% (< 5%).
- If the true ORR is 30% for TNBC (i.e. in the clinically significant efficacy range), the probability of observing an ORR  $\geq 20\%$  is 94.2%.

**Table 10-3 Operating characteristics of the design (LAG525+PDR001)**

True ORR	Probability to observe <3 responses in first 20 patients	Groups 6,8,9,12,13,15: NSCLC, renal and mesothelioma	Groups 7 & 10: melanoma
		probability to observe an ORR $\geq$ 30% with 40 patients	probability to observe an ORR $\geq$ 45% with 40 patients
15%	40.5%	1.2%	<0.1%
20%	20.6%	8.7%	<0.1%
30%	3.5%	55.8%	3.2%
40%	0.4%	92.8%	31.1%
45%	0.1%	98.2%	56.1%
55%	<0.1%	>99.9%	92.3%

**Table 10-4 Operating characteristics of the design (LAG525 + PDR001)**

True ORR	Probability to observe <2 responses in first 20 patients	Groups 14, 16: TNBC
		probability to observe an ORR $\geq$ 20% with 40 patients
10%	39.2%	4.1%
15%	17.6%	24.1%
20%	6.9%	55.7%
25%	2.4%	81.3%
30%	0.8%	94.2%
40%	0.1%	99.8%

## 10.9 Power for analysis of key secondary variables

Not applicable.

## 11 Ethical considerations and administrative procedures

### 11.1 Regulatory and ethical compliance

This clinical study was designed, shall be implemented and reported in accordance with the ICH Harmonized Tripartite Guidelines for Good Clinical Practice, with applicable local regulations (including European Directive 2001/20/EC and US Code of Federal Regulations Title 21), and with the ethical principles laid down in the Declaration of Helsinki.

### 11.2 Responsibilities of the investigator and IRB/EC/REB

The protocol and the proposed informed consent form must be reviewed and approved by a properly constituted Institutional Review Board/Independent Ethics Committee/Research Ethics Board (IRB/IEC/REB) before study start. Prior to study start, the investigator is required to sign a protocol signature page confirming his/her agreement to conduct the study in accordance with these documents and all of the instructions and procedures found in this protocol and to give access to all relevant data and records to Novartis monitors, auditors, Novartis Clinical Quality Assurance representatives, designated agents of Novartis, IRBs/IECs/REBs and regulatory authorities as required.

### **11.3 Informed consent procedures**

Eligible patients may only be included in the study after providing written (witnessed, where required by law or regulation), IRB/IEC/REB-approved informed consent or, if incapable of doing so, after such consent has been provided by a legally acceptable representative of the patient. In cases where the patient's representative gives consent, the patient should be informed about the study to the extent possible given his/her understanding. If the patient is capable of doing so, he/she should indicate assent by personally signing and dating the written informed consent document or a separate assent form.

Informed consent must be obtained before conducting any study-specific procedures (i.e. all of the procedures described in the protocol). The process of obtaining informed consent should be documented in the patient source documents. The date when a subject's Informed Consent was actually obtained will be captured in their CRFs.

Novartis will provide to investigators, in a separate document, a proposed informed consent form (ICF) that is considered appropriate for this study and complies with the ICH GCP guideline and regulatory requirements. Any changes to this ICF suggested by the investigator must be agreed to by Novartis before submission to the IRB/IEC/REB, and a copy of the approved version must be provided to the Novartis monitor after IRB/IEC/REB approval.

Women of child bearing potential should be informed that taking the study medication may involve unknown risks to the fetus if pregnancy were to occur during the study and agree that in order to participate in the study they must adhere to the contraception requirement for the duration of the study. If there is any question that the patient will not reliably comply, they should not be entered in the study.

[REDACTED]

